EN-CAMHS 1 stakeholders recommended we implement a digital solution to address the current problems of poor communication, missing information, poor data quality and lack of guidance for families about what to expect of the referral journey. The design and development of the digital tool will specifically address the accessibility needs of referrers. We intend to explore issues of digital accessibility in the consultations (WP1) and in the co-design workshops with participants. We shall also consider the three key elements of digital exclusion: lack of digital access; lack of digital skills; lack of confidence to use digital. We will explore these challenges in the co-design workshops, with stakeholders in consultation and with our advisory groups. The digital tool will supplement rather than supplant traditional modes of referral; traditional (e.g. paper based) modes of referral will remain. However, we anticipate that our digital tool will enable more people to make more successful referrals than before.

We shall also **generate new knowledge** about the patterns of referrals into CAMHS, by automating data collection through the digital tools and thereby enabling services and NHS England to understand referral and treatment data in greater detail than ever before. We see **enormous potential** in this project and its learnings/outputs for cross-pollination to **other services experiencing similar problems**.

1. Referrals overwhelming CAMHS

- We **cannot** increase CAMHS staff levels or change what it can provide.
- We **can** make the referral process work better and with greater satisfaction for referrers and for those being referred.
- We **can** increase confidence in CAMHS alternatives and increase follow-through into CAMHS alternatives.
- We **can** help CAMHS prioritise the needs of those it is designed to help.

2. Quality of referrals is poor

- We **can** provide clear, accessible guidelines to make appropriate referrals.
- We **can** validate input on the referral form and ensure all required information is completed pre-submission.
- We **can** raise awareness about what a good referral is.
- We **can** educate people about common referral mistakes.

3. Poor experience of referral

- We **can** explain the referral process clearly.
- We **can** outline key steps in the referral journey and inform people about the expected waiting times for the local CAMHS triage process.

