- Discovery [38]: The discovery phase will draw heavily on the findings of ENCAMS 1 and of Work Package 1 of this project. We shall translate these findings into outputs that can be disseminated widely including User Personas (to indicate the profiles of different referrers who will use the system) and User Journey Maps (to show how people will interact with the system at each stage of the process).
- Alpha [39]: Our senior designer will produce prototypes and wireframes to demonstrate the flow of the digital tool in this phase for feedback and review by workshop participants.
- Beta [40]: During this phase, we shall ask at least 5 healthy volunteers to try out the newly-developed tool to ensure it has no critical or major defects and is ready for use in the evaluation in WP3.
- Live [41]: The live version of the platform will be demonstrated in a co-design workshop available for participants to try and provide feedback.

A priority for the digital tool is to be inclusive and accessible to all. We will work collaboratively with our stakeholder groups during the co-design phase to ensure we maximise the accessibility of the tool. From EN-CAMHS 1 we already know that supporting access to translated materials is an important requirement. We aim to go well above and beyond the WCAG 2.2 standards [31] to ensure that the tool we develop has as wide a reach as possible. We shall also beta-test the accessibility with a Digital Accessibility Working Group.

Work Package 3 (WP3): (KMA, PW, VB, LAC, PB, RE, PB) Months 12-24 - Evaluation of Implementation

We aim to:

- Evaluate implementation of the new digitally-enhanced referral process with 60 key referrers.
- Explore the potential, enablers and barriers of embedding a new CAMHS referral mechanism via semi-structured qualitative interviews with 25 referrers.
- Develop a blueprint and toolkit for CAMHS to implement the referral tool.
- Understand if and how the tool enhances the CAMHS referral process.

A mixed-methods, non-randomised evaluation of implementation with 60 CAMHS referrers across 5-8 CAMHS. CAMHS sites and referrers will be chosen to reflect the diversity of the current CAMHS landscape. 9 CAMHS sites have indicated their support for working with us on the evaluation. We shall evaluate usage and acceptability data collected from referrers which combine quantitative data on engagement and usage with qualitative data from semi-structured interviews with 25 referrers.

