We shall use the NASSS-CAT toolkit [32] to guide the implementation and evaluation of the digital tool across CAMHS sites. This entails running a NASSS-CAT workshop with key stakeholders from each CAMHS service in order to introduce and complete the assessment as well as create a risk management and mitigation plan. The workshop will identify gaps in information that will need to be identified and incorporated. Once this is done, the risk plan will be regularly reviewed throughout the implementation process. Insights from this will be turned into an implementation toolkit that sets out a standardised evidence-based approach along with common risks and how they can be managed or mitigated. We shall also use the NASSS-CAT implementation toolkit to explore the potential, enablers and barriers of embedding a new CAMHS referral mechanism across different types of referrers and across CAMHS with various configurations. The NASSS-CAT toolkit will be used to guide implementation discussions with key stakeholders. Specifically, we will use the NASSS framework to address key considerations for the implementation digital transformation covering the key NASSS areas: the illness/condition in question; the technology; the value proposition; the intended adopters; the organisation; external context for innovation. The questions from the NASSS-CAT toolkit on these areas will be tailored for the EN-CAMHS project and used to structure the topic guides for interviewers with referrers.

We shall collect referral data from each referrer and from the CAMHS site referred into. We shall collect number of referrals made via the digital tools and numbers made by traditional referral mechanisms. We shall collect usage and engagement data with the tool, including numbers of referrals completed to an endpoint (either referral sent to CAMHS or to alternative help). We shall collect data on accepted/rejected referrals made by participant referrers to CAMHS using a) the tool and b) traditional modes of referral. Co-design workshops with each CAMHS provider will help us understand which data can be captured, and how each provider records the data.

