method and we will explore whether this differs between type of referrer. We shall explore 'effective engagement' with the tool: the ability of referrers to complete a successful referral with the tool. A successful referral can mean either a referral to CAMHS or to an alternative source of support for the CYP. We shall analyse the rate of successful referrals made using the tools against those made using traditional referral processes.

Qualitative data analysis: We will conduct qualitative interviews (n=25) with referrers who have used the digital tool to highlight any potential barriers to implementation. Additionally, WP3 Qualitative data analysis: Anonymised transcripts will be analysed using NATCEN Framework Analysis methodology set out by Ritchie and Spencer [43], outlined in Ritchie et al. [44], and using Nvivo 12, as this has a Framework Matrices Tool [45], allowing for both inductive and deductive coding. Coders will meet regularly to discuss codes and develop a provisional framework. During constant comparison of new data, this provisional framework will be amended to accommodate new codes and remove old codes that become superfluous. The final coding framework will be presented to the study advisory group to ensure interpretations of data remain grounded in the experience of mental health services. Analysis will occur in parallel to data collection. The whole team will agree when data saturation has occurred.

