6.2 Sampling

6.2.1 Size of sample

In WP1, we shall recruit 60 key CAMHS stakeholders (CYP, parents and carers, key referrers and CAMHS professionals) to 6 focus groups (10 participants per group).

In WP2, we shall recruit 5-8 CAMHS providers, with 5-8 members of Trust staff from each provider to participate in a workshop (25-64 staff in total). 2 1-hour co-design workshops will also be held with 25 key referrers in each group. A maximum of 10 stakeholders shall be recruited to form the Digital Accessibility Working Group (n=10 CYP/families and professional referrers); a group formed from the project with characteristics derived from accessibility needs identified in the stakeholder co-design groups and from EN-CAMHS 1. This group shall meet twice during the co-design process to review the tool and suggest accessibility enhancements. Every effort will be made to incorporate suggestions made by this group into the digital tool, within the time and resource limitations of the project

In WP3, we shall recruit 60 key referrers across all sites for quantitative data collection. 25 of the key referrers will also participate in qualitative semi-structured interviews.

The sample size across the project will be made up of:

- WP1 - 6 focus groups - we aim to recruit 60 stakeholders (6-10 per group).
- WP2 - onboard 5-8 CAMHS providers, 1-hour co-design workshop with each provider (n=25), Accessibility working group n=10. 2 co-design workshops with up to 25 participants in each (n=50).
- WP3 - 60 referrers to use the tool, semi-structured interviews with 25 referrers.

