6.2.2 Sampling technique

In WP1 and WP2, we shall use purposive sampling to recruit a diverse group of CAMHS stakeholders and Trust staff for focus groups.

In WP3, we shall use purposive sampling to include a diversity of referrers. We shall aim for diversity in terms of: type of referrer (GP, school, self-referrer, social care); CAMHS configuration (provision of service; location of CAMHS urban/rural) and by key individual characteristics of the referrer (age, ethnicity, spoken language etc). We shall aim to make the sample of referrers representative of the proportions of the different referrers that refer into CAMHS. That would mean more GPs than other referrers. The diversity of CAMHS configuration will be drawn from the data from EN-CAMHS 1 and with respect to relevant recent changes to the CAMHS landscape identified in WP1.

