8.2 Outputs

Key indicators of success will be defined by the following criteria:

- Digital referral platform successfully tested across minimum 5 CAMHS.
- Stakeholders successfully recruited to roundtable events and prioritisation of features consultation.
- CAMHS referral technical standards defined.
- Co-design of digital tool completed with outputs produced and published.
- Quantitative referral data collected and analysed from CAMHS sites. A reduction in the proportion of unsuccessful referrals is achieved when made through the ENCAMS platform compared to the usual referral processes.
- Following AMUsEd framework, engagement and usage metrics with the digital platform demonstrate that the platform is usable and acceptable to referrers.
- Qualitative intervention data successfully collected and analysed. Qualitative interviews demonstrate usability and acceptability of the platform to referrers and key stakeholders, including GPs, school staff, health and educational professionals and CYP and families/carers themselves. Qualitative interviews demonstrate a preference for the platform by referrers and key stakeholders, including GPs, school staff, health and educational professionals and CYP and families/carers themselves.
- Evaluation successfully completed.
- Sustainability plan developed that secures future plan for the CAMHS digital tool supported for use within the NHS.

Specific outputs for WP1

- Report detailing the changing CAMHS landscape (from roundtables) and how the digital tool aligns with newly configured CAMH services.
- Clear set of priorities and requirements for the revised CAMHS referral process, ranked by Must Have, Should Have, Could Have and Won't Have (MoSCoW) to enable the technical build in Work Package 2.
- A set of technical referral standards for the digital tool for development in WP2.

Finally, we aim to produce 4 peer-reviewed academic publications during the project.

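### The success indicator rests on a crude tool-versus-traditional difference that referrer and site mix alone can create or hide

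*Protocol*

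**What the plan says.** Research question 6 (section 3) asks how success rates with the tool compare with traditional referral. The analysis sentence in section 4.2 is: "We shall analyse the rate of successful referrals made using the tools against those made using traditional referral processes". It says nothing more about how the comparison will be made.

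Section 8.2 then lists this among the key indicators of success: "A reduction in the proportion of unsuccessful referrals is achieved when made through the ENCAMS platform compared to the usual referral processes". No adjustment, stratification or degree of precision is attached.

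The design around the comparison is as follows.

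- Section 4.1 describes "A mixed-methods, non-randomised evaluation of implementation with 60 CAMHS referrers across 5-8 CAMHS".
- Section 2 states: "The digital tool will supplement rather than supplant traditional modes of referral; traditional (e.g. paper based) modes of referral will remain".
- Section 6.2.1 states that "we shall recruit 60 key referrers across all sites for quantitative data collection". Section 6.2.2 seeks diversity of referrer type and CAMHS configuration, and adds: "That would mean more GPs than other referrers". Section 5 selects sites to differ in location, population and service configuration.
- Section 4.1 provides the data: "We shall collect referral data from each referrer and from the CAMHS site referred into", and "We shall collect data on accepted/rejected referrals made by participant referrers to CAMHS using a) the tool and b) traditional modes of referral".

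Section 3 says that there are no primary or secondary outcomes because this is a feasibility study. Section 6.3.1 says that hypothesis testing is not the aim.

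**The concern.** A crude rate for each route is an average over whichever referrers and sites happened to use that route. Nothing in the protocol assigns the route, and the sample is built to be heterogeneous. If uptake of the tool and the chance of acceptance both vary between referrers or sites, the two crude rates describe different mixes of referrers. Their difference then combines any tool effect with that mix.

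The indicator in section 8.2 asks only whether the unsuccessful proportion is lower with the tool. The study could declare success because careful referrers, or sites that accept more readily, took to the tool. It could equally miss a real benefit because referrers who struggle with the process preferred a guided form. The claim would then support the sustainability and national roll-out work in WP4.

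The data in section 4.1 are recorded by referrer and by route, so a comparison that removes differences between referrers needs no new data.

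**Working it through.** The protocol gives no interval, standard error, effect size or power for this comparison, so there is no figure to reproduce. The checks below show how large the effect of mix could be.

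**Inputs.** From the protocol: 60 referrers and 5-8 sites. Success is taken as about 75%, because the Background puts unsuccessful referrals nationally at almost a quarter. Assumed: referrals per referrer, within-referrer correlation, and how uptake varies between referrers.

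**Check 1: spurious difference by arithmetic.** Take two equal halves of referrers with equal volumes and no tool effect. One half has success rate *h* and sends share *s* of its referrals through the tool. The other half has rate *l* and sends share 1 − *s*.

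- Tool rate = *s·h* + (1 − *s*)·*l*
- Traditional rate = (1 − *s*)·*h* + *s·l*
- Difference = (2*s* − 1)(*h* − *l*)

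| Uptake | 80% vs 70% success | 85% vs 65% success |
|---|---|---|
| 50/50 by everyone | 0 × 10 = 0 points | 0 × 20 = 0 points |
| 80/20 vs 20/80 | 0.6 × 10 = 6 points | 0.6 × 20 = 12 points |
| One route only | 1.0 × 10 = 10 points | 1.0 × 20 = 20 points |

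If the weaker half are the heavier users, every sign reverses. Within each half the true difference is zero throughout.

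**Check 2: simulation with no tool effect.** 1,500 studies per setting, 60 referrers averaging about 10 referrals with skewed volumes, and 75% mean success. Within-referrer correlation (ICC) is 0.05, 0.10 or 0.20, and tool share is spread freely between referrers.

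| Correlation of uptake with referrer quality | Mean crude difference (ICC 0.05 / 0.10 / 0.20) |
|---|---|
| −0.3 | about −3 to −6 points across the three |
| 0 | about 0 |
| 0.3 | +3.2 / +4.7 / +6.1 points |
| 0.5 | +5.5 / +7.5 / +10.3 points |

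At correlations of 0.3 to 0.5, a rule that asks only for a positive crude difference is met in about 79-98% of studies. The reference value is about half, because with no effect and no correlation the sign of the difference is a coin toss. The within-referrer (Mantel-Haenszel) difference averages 0.0 in these settings. Its standard deviation is about 4 to 4.5 points, against about 3.9 to 5.3 for the crude difference.

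**Check 3: does ignoring clustering overstate precision?** For a difference of two crude proportions with within-referrer correlation ρ, the design effect is

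(1 − ρ) + ρ·Σ(n_Ti/N_T − n_Ci/N_C)² ÷ (1/N_T + 1/N_C).

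With 60 referrers, 10 referrals each and 300 per route, 1/N_T + 1/N_C = 2/300 = 0.00667.

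- Even split by everyone: the sum is 0, so the design effect is 1 − ρ. It runs from 0.98 to 0.80 for ρ = 0.02 to 0.20.
- 80/20 vs 20/80: the sum is 60 × (8/300 − 2/300)² = 0.024, and 0.024/0.00667 = 3.6. The design effect is 1 + 2.6ρ, which is 1.05, 1.26 and 1.52 for ρ = 0.02, 0.10 and 0.20.
- One route only: the sum is 60 × (10/300)² = 0.0667, and the ratio is 10. The design effect is 1 + 9ρ, which is 1.18, 1.90 and 2.80.

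The direction of the precision error therefore depends on uptake. An analysis that treated referrals as independent could give an interval that is too wide or too narrow.

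**The case against.** A reader might infer that the plan pools all referrals as if independent, that every referrer contributes to both routes, and that the precision is therefore overstated. The documents support none of these.

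- Section 4.2 names no unit of analysis, model, interval or test. Silence is not an assumption of independence, and handling of clustering may sit in an analysis plan that is not shown.
- Section 4.1 says that both routes are recorded for participating referrers, not that each uses both. Parents, carers and self-referrers may refer only once.
- No interval is planned, so there is no stated precision to overstate. Check 3 shows that the error could go either way.

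It is also fair to say that this is a feasibility study without outcome measures or hypothesis tests. The volumes, correlations and uptake patterns above are assumed, and the sign of the bias is unknown. Stratifying by referrer does not remove a referrer's case-by-case choice of route.

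All of that stands, and it narrows the point without removing it. The indicator is fixed in the protocol itself, in section 8.2, so an analysis plan would not by itself change what the protocol counts as success. Bias from mix does not depend on a test being run.

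**Conclusion.** The concern holds in this form: the protocol counts any observed reduction in unsuccessful referrals as success, in a non-randomised comparison with open choice of route and deliberately varied referrers and sites, and ties that indicator to no estimate that accounts for the mix.

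With no tool effect, the illustrative crude difference is about 3 to 10 points when uptake rises with referrer quality, and about 3 to 6 points the other way at a correlation of −0.3. It is zero if every referrer uses both routes equally. These sizes rest on about 10 referrals per referrer, an ICC of 0.05 to 0.20 and the assumed link between uptake and quality; the protocol states none of them. Against a national unsuccessful rate of almost a quarter, a shift of this size would change the conclusion. The change should be made, but nothing here shows that the study's data will be biased in a particular direction.

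**What to change.** **Section 4.2.** After the comparison sentence, state that the tool-minus-traditional difference in successful-referral proportion will be estimated stratified by referrer. Alternatively, use a referrer-level model that also accounts for site and referrer type, so that referrers who use one route still contribute. Give a 95% interval that allows for clustering by referrer. Show crude rates by route for description only.

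**Section 8.2.** Tie the indicator to that estimate and its interval rather than to any crude reduction. The interval matters because, with no effect, even an unbiased point estimate favours the tool about half the time. State that the comparison remains non-randomised because referrers may choose the route case by case.

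**Cost.** New wording and slightly more analysis, on data that section 4.1 already collects by referrer and route. Referrers who use only one route add nothing to a strictly within-referrer estimate. That may fall most on families and self-referrers, against the diversity aim, which is the reason to allow the model as an alternative. The model keeps these referrers, but for them it relies on adjustment between referrers.

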5 STUDY SETTING

This is a multi-site study. The referral data collection will involve 5-8 CAMHS sites from various regional providers. The collaborating sites will be selected to: target the areas of high need for CYP mental health; reflect diversity in terms of urban/rural locations; ethnicity of service user population; diversity in configuration of CAMHS services/CAMHS offer.

The stakeholder and Trust staff consultations, i.e. roundtables, focus groups, workshops and semi-structured interviews, will be held both virtually and face-to-face. Virtual consultations will be facilitated via Microsoft Teams. If any sessions are held in person, these will be held at different locations to ensure they are as accessible as possible, for example, central locations in both the South and North of England.

Quantitative data reflecting usage and engagement will be collected using inbuilt analytics.

6 SAMPLE AND RECRUITMENT

6.1 Eligibility Criteria

6.1.1 Inclusion criteria

Throughout the project, participants will be included if they are:

- Aged 16+.
- CAMHS Stakeholders who have experience with the CAMHS referral process since 2019, these may include:
 - CAMHS Staff: we will include any staff who currently work in CAMHS services.
 - Collaborators: We will include collaborators who have direct experience of the current referral process for CAMHS.
 - CYP: We will be recruiting CYP who have been referred to CAMHS regardless of whether they were accepted into the service or not.

- Key referrers: We would ask that these individuals have had experience referring CYP to CAMHS, regardless of how many times.
- Parents/carers: we will ask parents/carers who have experience of their child or a child in their care having been referred to CAMHS, regardless of the outcome of the referral.
- CAMHS Commissioners: We will ask Commissioners who understand the current CAMHS referral processes locally or nationally, and who are involved in the funding process.
- Mental Health Leads: We will invite people with a strategic overview of the CAMHS referral process locally or nationally to share their experiences of the referral process.
- Any individuals identified through earlier WPs as key to the CAMHS referral process.
- Able to provide informed consent.
- Be proficient in English.

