4.1 Data Collection

Work Package 1 (WP1), Months 3-12 (Leads: MQ, PW, PB) - Requirements Prioritisation

Aims:

- We shall hold 2 x roundtable events (Manchester and London) to gather feedback and input from senior stakeholders (e.g. NHS England senior leaders; commissioners, CAMHS leaders).
- With our partner MQ, we shall conduct 6 stakeholder focus groups with CYP, families/carers and professionals including GPs, to collaboratively prioritise requirements (identified in EN-CAMHS 1) for the revised digital tool. We aim to recruit up to 10 stakeholders per group, therefore 60 participants in total. We shall use the MoSCoW prioritisation method [29] collaboratively as we have done in a number of other NIHR funded digital health projects. As part of this prioritisation process, each of the existing 11 interactive CAMHS referral forms created by individual CAMHS in England will be rated using the System Usability Scale [30] and using criteria from the EN-CAMHS 1 focus groups (e.g. navigability, clarity of language, accessibility).

The technical project team will use the information from the roundtable and stakeholder meetings about the broader technical mental health landscape alongside their expert digital health software knowledge to develop a set of technical standards relevant for the CAMHS referral process. The costed software engineer will align with and extend existing NHS referral standards and interoperability standards to achieve this aim.

Work Package 2 (WP2) (PW, RE, JEC, Digital Health Software Team, VB): Months 3-12 - Co-Design and Tool Implementation

Aims:

- Onboard 5-8 CAMHS providers (with different characteristics and served populations) who are willing and can support an evaluation of the digitally-enhanced CAMHS tool in collaboration with our partners, NHS England.
- Workshops with 5-8 Trust staff from each provider.
- Co-design the tool with CAMHS stakeholders (2 x 1-hour workshops with 25 referrers).

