6.1.2 Exclusion criteria

- Participants must be able to speak English at a basic level.
- Participants must have good internet access to take part in the online consultations.
- Participants have not had experience with the CAMHS referral process.

We will inform participants during the consent process (i.e. in the PIS and subsequent discussions) that there may be discussion which they could find upsetting, and we have a distress protocol in place for if anyone needs additional support, but that this should be considered when agreeing to take part in the study.

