6.3 Recruitment

6.3.1 Sample identification

In WP1, we shall hold a combination of stakeholder specific and mixed stakeholder groups. Attendees can choose which type of group they feel most comfortable attending. Across the 6 focus groups we aim to recruit 60 participants representing a diversity of referrer type (CYP, GP, health, social care, educational professional, CAMHS workers, families), and also designed to incorporate the diversity within each referrer type found in EN-CAMHS 1. Identification and recruitment of stakeholders will be extensively supported by our partner MQ.

In WP3, we shall recruit referrers from across the study CAMHS sites. Senior stakeholder collaborators will be consulted to ensure the project achieves the most appropriate mix of CAMHS providers to optimise widespread applicability of the new tool. We shall work with 60 referrers to test the new referral process. We shall specifically aim to ensure appropriate diversity to test if the translated and culturally-sensitive materials we develop are fit for purpose.

We have not used power calculations for detecting effect sizes in this evaluation, as hypothesis testing is not the aim. Our aims are to 1) recruit participants to test different user experiences (opportunities and challenges) that arise as a result of using tool and; 2) to capture a diversity of: referrer types (GPs, school staff, social care professionals, parents/carers); within-referrer characteristics (age, gender, ethnicity, dis/ability); CAMHS provider (CAMHS configuration; rural/urban). Our purposive sampling approach will be targeted at maximising the diversity of referrers and CAMHS sites and supporting accessibility testing of the tool. Our sampling strategy will be informed by our diversity data from EN-CAMHS 1 and by the stakeholders consultations in WP1.

Identification and recruitment of CAMHS professional stakeholders will be supported by our extensive network of CAMHS collaborators. Recruitment of key referrers is supported by our school and primary care collaborators, as well as links to key referrers provided by our CAMHS sites. We will not directly target individuals, just share adverts about the study around collaborating organisations and networks.

Recruitment of CYP and their families will be supported by our CAMHS networks, adverts on social media and websites, and our third sector collaborators (MQ, Calm Connections, Anna Freud Centre).

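### Nothing in the eligibility rules keeps people who helped design the tool out of the WP3 evaluation, or records that they were involved

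*Protocol*

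**What the plan says.** Section 6.1.1 opens with "Throughout the project, participants will be included if they are" and then gives one list of stakeholder types for the whole study. Two entries matter here: "Collaborators: We will include collaborators who have direct experience of the current referral process for CAMHS", and "Any individuals identified through earlier WPs as key to the CAMHS referral process". The exclusions in 6.1.2 concern English, internet access and lack of referral experience ("Participants have not had experience with the CAMHS referral process"). None concerns an earlier role in the project.

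On WP2, section 6.2.1 says "2 1-hour co-design workshops will also be held with 25 key referrers in each group", while section 4.1 has "Co-design the tool with CAMHS stakeholders (2 x 1-hour workshops with 25 referrers". A Digital Accessibility Working Group of up to 10 people, formed from within the project, reviews the tool twice. On WP3, section 6.2.1 takes 60 key referrers across all sites, 25 of whom are also interviewed.

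On recruitment, section 6.3.1 says "Recruitment of key referrers is supported by our school and primary care collaborators", with further links supplied by the CAMHS sites. Adverts are circulated in collaborating organisations and networks, and individuals are not approached directly.

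Section 8.2 lists nine success indicators. One is that usage metrics show the platform to be usable and acceptable. Another is that interviews show usability and acceptability, and further that "Qualitative interviews demonstrate a preference for the platform by referrers and key stakeholders".

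**The concern.** WP3 is where the protocol finds out how referrers perceive the tool (research question 4) and how they use it (research question 5). Someone who has commented on prototypes, tried a demonstrated version or had suggestions built in is not a first-time user. Such a person is likely to find the tool easier to use and may be better disposed towards it.

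Two things are at stake. Favourable findings on usability, acceptability and preference could partly reflect who was asked. And obstacles that a newcomer meets at first use, which the interviews are meant to bring out, could go unseen. Both matter although the study tests no hypothesis, because a descriptive or qualitative conclusion also depends on who supplies the data. If prior involvement is not recorded, a reader of the final report cannot judge how far this happened.

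**Working it through.** No sample-size or power figure bears on this point, so there is nothing of the plan's own to reproduce. The check compares the relevant sections and then bounds the overlap.

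**Can the same person be in WP2 and WP3?**
- Population: WP2 co-design and WP3 both draw on key referrers (6.2.1). Both include professionals, young people and families (4.1, 4.2).
- Sites: the providers named in 4.1 are provisionally confirmed for WP2 and WP3 together.
- Timing: WP2 runs in months 3 to 12 and WP3 in months 12 to 24 (4.1), so one follows the other.
- Sampling: the WP3 purposive frame covers referrer type, CAMHS configuration and personal characteristics (6.2.2). Independence from the tool is not among them.
- Exclusion: none applies (6.1.2).

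So a WP2 co-designer who refers into a study site meets every stated condition for WP3.

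**What exposure would that person have had?** Under 4.1, workshop participants review prototypes, and the live version is shown in a co-design workshop for them to try. The accessibility group reviews the tool twice, and the team undertakes to adopt its suggestions as far as it can.

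**How large could the overlap be?** Inputs from 6.2.1 and 4.1:
- co-designers, C: 25 if the same people attend both workshops, 50 if the two groups are distinct
- accessibility group, A: at most 10
- WP3 users: 60
- interviewees: 25

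| Quantity | Formula | C = 25 | C = 50 |
|---|---|---|---|
| Maximum share of the 60 users, co-designers only | C / 60 | 25/60 = 42% | 50/60 = 83% |
| Maximum share, adding a wholly separate accessibility group | min(C + A, 60) / 60 | 35/60 = 58% | 60/60 = 100% |
| Maximum share of the 25 interviewees | min(C, 25) / 25 | 25/25 = 100% | 25/25 = 100% |
| Minimum share of either | no overlap is required | 0% | 0% |

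The maxima assume that every earlier participant refers into a study site, volunteers again and fits the purposive frame. The document contains nothing from which a point between floor and ceiling could be estimated.

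**Where would it enter the conclusions?** Two of the nine indicators in 8.2 are directly exposed: the one on usage metrics and the one on interviews. Preference is judged from interviews only. The indicator on unsuccessful referrals rests on referral records and depends less on opinion. However, 4.2 also examines whether referrers can complete a successful referral with the tool, and practice could help with that.

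**The case against.** The strongest reply is that 6.1.1 is an umbrella list and that WP3 is narrower. It takes key referrers only (6.2.1), from the study sites (6.3.1), chosen purposively in rough proportion to who refers (6.2.2). A reader might infer from the collaborator entry that the project's partners will evaluate their own tool. The text does not support that. A collaborator reaches WP3 only by also being a referrer at a study site, and 6.1.1 does not define the term, although elsewhere the protocol uses it for the project's own partners. This part of the reply stands, and it makes the co-designers the more important route.

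A reader might also take the entry on people identified through earlier work packages as express permission to re-use WP2 participants. It can as naturally mean newly recognised kinds of stakeholder. The overlap is therefore unaddressed; it is not planned.

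Third, recruitment is by advert without targeting individuals, and the co-design workshops are not said to be confined to the study sites. Both make large overlap less likely. Neither prevents it, because the adverts go round the collaborating networks.

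Fourth, this is feasibility work without primary or secondary outcomes, and informed users can also report barriers. That limits the consequence. It does not answer the point about first-use barriers, or the success indicators in 8.2.

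Finally, a blanket exclusion could work against the diversity and accessibility aims in 6.3.1. That is a fair objection to a bar, and the fix below avoids one.

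**Conclusion.** The concern holds as an unguarded possibility. The protocol neither prevents nor records the entry into WP3 of people who shaped the tool or had already been shown it. The extent runs from none to 25 to 50 of the 60 users, and up to all 25 interviewees. It would be wrong to read the 42% to 83% as an expected share: these are ceilings, and the floor is zero.

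The direction of any bias is probably favourable to the tool, on the assumption that familiarity and authorship make people more positive and more proficient. Its size cannot be stated. A reader might want a figure in percentage points, but the protocol judges preference from framework analysis of interviews and calculates no such percentage. Nor does the point undermine every success indicator, since most of the nine in 8.2 do not depend on users' opinions.

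This is a modest weakness in the evaluation that can be removed cheaply before WP3 recruitment.

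**What to change.** In section 6.1, state that the collaborator category applies to WP1 and WP2 only. For WP3, add one screening question on earlier involvement: as collaborator, co-design workshop participant, beta tester, accessibility group member or advisory group member. Beta testers and advisory members are included because they too may have seen or influenced the tool.

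Fill WP3 places, and above all the 25 interviews, with referrers new to the tool where they are available. Where others are admitted to meet the diversity or accessibility aims, report usage, usability, acceptability and preference with and without them. In section 8.2, say that the acceptability and preference indicators are judged on participants new to the tool.

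The cost is an amendment to the wording of 6.1 and 8.2, one extra screening item, one extra breakdown in the report and a somewhat smaller pool of ready volunteers. Admitting prior contributors where needed softens the last of these.
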